8.3 INSTITUTIONAL REVIEW BOARD OR ETHICS COMMITTEE

This protocol, the Informed Consent Forms, any information to be given to the patient, and relevant supporting information must be submitted to the IRB/EC by the Principal Investigator and reviewed and approved by the IRB/EC before the study is initiated. In addition, any patient recruitment materials must be approved by the IRB/EC.

The Principal Investigator is responsible for providing written summaries of the status of the study to the IRB/EC annually or more frequently in accordance with the requirements, policies, and procedures established by the IRB/EC. Investigators are also responsible for promptly informing the IRB/EC of any protocol amendments (see Section 9.7).

In addition to the requirements for reporting all adverse events to the Sponsor, investigators must comply with requirements for reporting serious adverse events to the local health authority and IRB/EC. Investigators may receive written IND safety reports or other safety-related communications from the Sponsor. Investigators are responsible for ensuring that such reports are reviewed and processed in accordance with health authority requirements and the policies and procedures established by their IRB/EC, and archived in the site's study file.

8.4 CONFIDENTIALITY

The Sponsor maintains confidentiality standards by coding each patient enrolled in the study through assignment of a unique patient identification number. This means that patient names are not included in data sets that are transmitted to any Sponsor location.

Patient medical information obtained by this study is confidential and may be disclosed to third parties only as permitted by the Informed Consent Form (or separate authorization for use and disclosure of personal health information) signed by the patient, unless permitted or required by law.

Medical information may be given to a patient's personal physician or other appropriate medical personnel responsible for the patient's welfare, for treatment purposes.

Given the complexity and exploratory nature of exploratory biomarker analyses, data derived from these analyses will generally not be provided to study investigators or patients unless required by law (with the exception of the report from Foundation Medicine). The aggregate results of any conducted research will be available in accordance with the effective Sponsor policy on study data publication (see Section 9.6).

Data generated by this study must be available for inspection upon request by representatives of national and local health authorities, Sponsor monitors, representatives, and collaborators, and the IRB/EC for each study site, as appropriate.

Study data, which may include data on genomic variants, may be submitted to government or other health research databases or shared with researchers, government agencies, companies, or other groups that are not participating in this study. These data may be combined with or linked to other data and used for research purposes, to advance science and public health, or for analysis, development, and commercialization of products to treat and diagnose disease. In addition, redacted Clinical Study Reports and other summary reports will be provided upon request (see Section 9.6).

8.5 FINANCIAL DISCLOSURE

Investigators will provide the Sponsor with sufficient, accurate financial information in accordance with local regulations to allow the Sponsor to submit complete and accurate financial certification or disclosure statements to the appropriate health authorities.

Investigators are responsible for providing information on financial interests during the course of the study and for 1 year after completion of the study (see definition of end of study in Section 3.2).

9. STUDY DOCUMENTATION, MONITORING, AND ADMINISTRATION

9.1 STUDY DOCUMENTATION

The investigator must maintain adequate and accurate records to enable the conduct of the study to be fully documented, including, but not limited to, the protocol, protocol amendments, Informed Consent Forms, and documentation of IRB/EC and governmental approval. In addition, at the end of the study, the investigator will receive the patient data, including an audit trail containing a complete record of all changes to data.

9.2 PROTOCOL DEVIATIONS

The investigator should document and explain any protocol deviations. The investigator should promptly report any deviations that might have an impact on patient safety and data integrity to the Sponsor and to the IRB/EC in accordance with established IRB/EC policies and procedures. The Sponsor will review all protocol deviations and assess whether any represent a serious breach of Good Clinical Practice guidelines and require reporting to health authorities. As per the Sponsor's standard operating procedures, prospective requests to deviate from the protocol, including requests to waive protocol eligibility criteria, are not allowed.

9.3 MANAGEMENT OF STUDY QUALITY

The Sponsor will implement a system to manage the quality of the study, focusing on processes and data that are essential to ensuring patient safety and data integrity. Prior to study initiation, the Sponsor will identify potential risks associated with critical trial processes and data and will implement plans for evaluating and controlling these risks. Risk evaluation and control will include the selection of risk-based parameters (e.g., adverse event rate, protocol deviation rate) and the establishment of quality tolerance limits for these parameters prior to study initiation. Detection of deviations from quality tolerance limits will trigger an evaluation to determine if action is needed. Details on the establishment and monitoring of quality tolerance limits will be provided in a Quality Tolerance Limit Management Plan.

9.4 SITE INSPECTIONS

Site visits will be conducted by the Sponsor or an authorized representative for inspection of study data, patients' medical records, and eCRFs. The investigator will permit national and local health authorities; Sponsor monitors, representatives, and collaborators; and the IRBs/ECs to inspect facilities and records relevant to this study.

9.5 ADMINISTRATIVE STRUCTURE

This trial will be sponsored and managed by F. Hoffmann-La Roche Ltd. The Sponsor or delegate will provide clinical operations management, data management, and medical monitoring.

Approximately 90 sites globally will participate to enroll approximately 215 patients. Randomization will occur through an IxRS.

Central facilities will be used for certain study assessments throughout the study (e.g., specified laboratory tests, biomarker and PK analyses), as specified in Section 4.5. Accredited local laboratories will be used for routine monitoring; local laboratory ranges will be collected.

A Steering Committee (SC) will provide scientific oversight for the trial. Details on the composition and mandate of the SC will be provided in the SC Charter.

9.6 DISSEMINATION OF DATA AND PROTECTION OF TRADE SECRETS

Regardless of the outcome of a trial, the Sponsor is dedicated to openly providing information on the trial to healthcare professionals and to the public, at scientific congresses, in clinical trial registries, and in peer-reviewed journals. The Sponsor will comply with all requirements for publication of study results. Study data may be shared with others who are not participating in this study (see Section 8.4 for details), and redacted Clinical Study Reports and other summary reports will be made available upon request. For more information, refer to the Roche Global Policy on Sharing of Clinical Trials Data at the following website:

www.roche.com/roche_global_policy_on_sharing_of_clinical_study_information.pdf

The results of this study may be published or presented at scientific congresses. For all clinical trials in patients involving an IMP for which a marketing authorization application has been filed or approved in any country, the Sponsor aims to submit a journal manuscript reporting primary clinical trial results within 6 months after the availability of the respective Clinical Study Report. In addition, for all clinical trials in patients involving an IMP for which a marketing authorization application has been filed or approved in any country, the Sponsor aims to publish results from analyses of additional endpoints and exploratory data that are clinically meaningful and statistically sound.

The investigator must agree to submit all manuscripts or abstracts to the Sponsor prior to submission for publication or presentation. This allows the Sponsor to protect proprietary information and to provide comments based on information from other studies that may not yet be available to the investigator.

In accordance with standard editorial and ethical practice, the Sponsor will generally support publication of multicenter trials only in their entirety and not as individual center data. In this case, a coordinating investigator will be designated by mutual agreement.

Authorship will be determined by mutual agreement and in line with International Committee of Medical Journal Editors authorship requirements. Any formal publication of the study in which contribution of Sponsor personnel exceeded that of conventional

monitoring will be considered as a joint publication by the investigator and the appropriate Sponsor personnel.

Any inventions and resulting patents, improvements, and/or know-how originating from the use of data from this study will become and remain the exclusive and unburdened property of the Sponsor, except where agreed otherwise.

9.7 PROTOCOL AMENDMENTS

Any protocol amendments will be prepared by the Sponsor. Protocol amendments will be submitted to the IRB/EC and to regulatory authorities in accordance with local regulatory requirements.

Approval must be obtained from the IRB/EC and regulatory authorities (as locally required) before implementation of any changes, except for changes necessary to eliminate an immediate hazard to patients or changes that involve logistical or administrative aspects only (e.g., change in Medical Monitor or contact information).

Appendix 1 Schedule of Activities

	Screening ^a	Window of Opportunity ^b		Neoadjuvant Treatment ^c						Surgery ^d	End of Study ^e
Cycle (28-day cycle)		0		1		2		3	4		
Days	-28 to -1	D1	Biopsy ^f D15 (+1D)	D1 (+3D)	D15 (±3D)	D1 (±3D)	D15 (±3D)	D1 (±3D)	D1 (±3D)		28 D (±3D)
Informed consent ^g	x										
Demographic data	x										
Medical history and baseline conditions	x										
PRO-CTCAE ^h				x		x		x	x		
CTSQ ^h									x		
Vital signs ⁱ	x	x		x	x	x	x	x	x	x	x
Weight	x	x		x		x		x	x		x
Height	x										
Complete physical examination ^j	x										x
Limited physical examination ^k				x		x		x	x	x	
Breast and axilla assessment ^l	x	x		x		x		x	x	x	
Tumor staging ^m	x										
ECOG	x			x		x		x	x		x
ECG (12-lead) ⁿ	x	x		x		x		x	x	x	x
Hematology ^o	x			x	x	x	x	x	x	x	x
Chemistry ^p	x			x	x	x	x	x	x	x	x

Appendix 1: Schedule of Activities

	Screening ^a	Window of Opportunity ^b		Neoadjuvant Treatment ^c						Surgery ^d	End of Study ^e
Cycle (28-day cycle)		0		1		2		3	4		
Days	-28 to -1	D1	Biopsy ^f D15 (+1D)	D1 (+3D)	D15 (±3D)	D1 (±3D)	D15 (±3D)	D1 (±3D)	D1 (±3D)		28 D (±3D)
Coagulation (INR, aPTT, PT)	x										x
Fasting lipid panel ^q	x										x
FSH ^r	x										
Estradiol ^r	x										
Urinalysis ^s	x					x		x	x		x
GDC-9545 or anastrozole (QD Days 1–28 of each cycle)		Administered at clinic visits (Day 1 of each cycle); otherwise administered at home.									
Palbociclib administration (QD Days 1–21 of each cycle)				Administered at clinic visits (Day 1 of each cycle); otherwise administered at home.							
Medication diary ^t		Complete when medication is taken at home or at clinic visit.									
Ki67score assessment ^u	x		x							x	
Tumor assessment (ultrasound) ^v	x								x		
Plasma PK samples				See Appendix 2.							
Biomarker samples (blood and tissue)				See Appendix 2.							
Surgical treatment plan ^w										x	
Concomitant medications ^x	x ^x	x ^x	x	x		x		x	x		x
Adverse events ^y	x ^y	x ^y	x	x		x		x	x	x	x ^y

Appendix 1: Schedule of Activities

CTSQ=Cancer Therapy Satisfaction Questionnaire; D=day; ECOG=Eastern Cooperative Oncology Group; FSH=follicle-stimulating hormone; PK=pharmacokinetic; PO=oral; PRO=patient-reported outcome; PRO-CTCAE=Patient-Reported Outcomes Common Terminology Criteria for Adverse Events; QD=once a day.

Notes: On treatment days that coincide with clinic visits, all assessments should be performed prior to dosing unless otherwise specified.

- ^a Results of standard-of-care tests or examinations performed prior to obtaining informed consent and within 28 days prior to Day 1 may be used; such tests do not need to be repeated for screening, unless otherwise indicated.
- ^b Patients will receive either GDC-9545 30 mg PO QD or anastrozole 1 mg PO QD for 2 weeks.
- ^c Patients will receive GDC-9545 30 mg PO QD (Days 1–28/cycle) plus palbociclib 125 mg PO QD (Days 1–21/cycle) or anastrozole 1 mg PO QD (Days 1–21/cycle) plus palbociclib 125 mg PO QD (Days 1–21/cycle) for four cycles (16 weeks), for 28 days per cycle. Starting with Day 1 of Cycle 1, and on Day 1 of each 28-day cycle thereafter, study treatment will be administered in the clinic, after the study assessments.
- ^d Surgery will be performed within 14 days after the final treatment in the neoadjuvant treatment phase. If surgery is delayed, if the patient is not operable or will not undergo surgery for other reasons, or does not complete 16 weeks (four cycles) of combination therapy, an optional biopsy may be performed as a separate procedure within 2 days from the end of the combination treatment (see [Appendix 2](#)).
- ^e Patients who complete the study or who discontinue the study prematurely will return to the clinic for an end of study visit 28 (\pm 3) days after the final study treatment.
- ^f A fresh post-dose biopsy will be obtained on Day 15 (+ 1 day). Blood will be collected from the patient, along with additional samples (see [Section 4.5.10](#) and [4.5.12](#)).
- ^g Informed consent must be documented before any study-specific screening procedure is performed, and may be obtained more than 28 days before initiation of study treatment.
- ^h Questionnaires will be self-administered before the patient receives any information on disease status, prior to the performance of non-PRO assessments, and prior to the administration of study treatment (see [Section 4.5.14](#)).
- ⁱ Vital signs include respiratory rate, pulse rate, and systolic and diastolic blood pressure while the patient is in a seated position, and temperature.
- ^j Complete physical examination includes evaluation of the head, eyes, ears, nose, and throat, and the cardiovascular, dermatologic, musculoskeletal, respiratory, gastrointestinal, and neurologic systems.
- ^k Perform a limited, symptom-directed examination at specified timepoints or as clinically indicated.
- ^l Assessment of primary tumor and regional lymph nodes must be performed by physical examination at screening and prior to administration of each cycle of study treatment during neoadjuvant therapy (see [Section 4.5.6](#)).
- ^m Tumor staging procedures are based on routine clinical practice (see [Section 4.5.8](#)).

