- Assessed by the investigator to be unable or unwilling to comply with the requirements of the protocol

End of Study

The end of this study is defined as the date when the last patient, last visit, occurs or the date of Sponsor decision to end the study, whichever is earlier. The end of the study is expected to occur approximately 6 months after the last patient is enrolled.

Length of Study

The total length of the study, from screening of the first patient to the end of the study, is expected to be approximately 19 months.

Investigational Medicinal Products

The investigational medicinal products for this study are GDC-9545 (test product), anastrozole (comparator), and palbociclib.

Test Product (Investigational Drug)

During the window-of-opportunity phase (14 days), patients will receive either GDC-9545 30 mg orally (PO) once a day (QD) or anastrozole 1 mg PO QD as a single agent. During the window-of-opportunity phase, GDC-9545 and anastrozole can be taken with or without food at approximately the same time each day.

During the neoadjuvant treatment phase, GDC-9545 30 mg PO QD or anastrozole 1 mg PO QD will be administered on Days 1–28 of each 28-day cycle in combination with palbociclib 125 mg PO QD on Days 1–21 of each 28-day cycle for four cycles. Starting with Day 1 of Cycle 0 and on Day 1 of each 28-day cycle thereafter, study treatment will be administered in the clinic after the study assessments, as indicated in the schedule of activities. All other doses will be taken at home on all non-clinic visit days. If a GDC-9545 dose is missed, the dose should be made up unless the next dose is due within 6 hours.

GDC-9545, anastrozole, and palbociclib should be taken orally with food at approximately the same time each day as per study treatment regimen. If palbociclib switches to tablet formation, study treatments may be taken with or without food.

Statistical Methods

Primary Analysis

The primary efficacy endpoint for this study is Ki67 score change during the window-of-opportunity phase, defined as the mean change of Ki67 score from baseline to Week 2. Ki67 score will be centrally assessed and measured in percentage score. All Ki67 scores will be log-transformed before analysis, and 0.1 will be added to all raw Ki67 scores before log-transformation to handle zero raw Ki67 scores.

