4.3.2.2 Compliance

At the beginning of study participation by a patient, site study staff will provide the patient with detailed instructions and training for the handling and administration of study treatment. Patients will receive and should be instructed to complete a medication diary.

At each clinic visit, the medication diary as well as unused tablets or capsules and all containers or packaging (used or unused) of study treatment should be collected and reviewed for drug accountability.

Treatment compliance will be defined as the number of capsules or tablets taken divided by the expected number of capsules or tablets and reported as a percentage. In case of dose reductions, the expected number of capsules or tablets should reflect the new dose level. Capsules or tablets that are not returned will be considered to have been taken, unless otherwise specified in the patient's diary and/or eCRF. Note that dosing eCRFs should be completed using the following prioritization: 1) site pharmacy drug accountability logs (IMP disbursed minus IMP returned), 2) clinic visit patient interview notes, and 3) patient daily dosing diary.

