5.3.1 Adverse Event Reporting Period

Investigators will seek information on adverse events at each patient contact. All adverse events, whether reported by the patient or noted by study personnel, will be recorded in the patient's medical record and on the Adverse Event eCRF.

After informed consent has been obtained but prior to initiation of study drug, only serious adverse events caused by a protocol-mandated intervention (e.g., invasive procedures such as biopsies, discontinuation of medications) should be reported (see Section 5.4.2 for instructions for reporting serious adverse events).

After initiation of study drug, all adverse events will be reported until 28 days after final dose of study treatment.

Instructions for reporting adverse events that occur after the adverse event reporting period are provided in Section 5.6.

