6.5.1 Analyses of Exposure, Adverse Event, Laboratory, and Vital Sign Data

The frequency, nature, and severity of treatment-emergent adverse events, adverse events leading to death, adverse events leading to study drug discontinuation and dose modification, serious adverse events, and adverse events of special interest will be summarized by treatment arm. All deaths will be summarized. Selected laboratory data will be summarized by treatment received and grade compared with baseline, and measurements outside of the normal range will be identified. Relevant vital signs will be presented using summary statistics by treatment received. Drug exposure will also be summarized, including duration of treatment, cumulative dose, and dose intensity.

Treatment-emergent adverse events are defined as adverse events that occur after the first dose of study treatment. Adverse events will be summarized by mapped MedDRA preferred terms and appropriate MedDRA hierarchy. Adverse event severity will be graded according to NCI CTCAE v5.0. Multiple occurrences of the same event will be counted once at the maximum severity.

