Appendix 2 Schedule of Pharmacokinetic and Biomarker Samples

Visit	Timepoint	Sample Type
Screening (Day –28 to Day –1)	NA	Pre-treatment archival or fresh tumor tissue sample(s) for biomarkers ^a
		Freshly frozen OCT pretreatment tumor tissue sample (optional) ^b
Cycle 0 Day 1 (Window of Opportunity)	Predose	Plasma for biomarkers
		Blood for WGS ^c
	Predose ^d	GDC-9545 PK (plasma)
	3 (+ 1) hours post-dose	GDC-9545 PK (plasma)
Cycle 0 Day 15 (± 1 D) (Biopsy)	Predose ^d	GDC-9545 PK (plasma)
	Postdose ^e	Fresh tumor tissue samples during treatment for biomarkers ^e
		Plasma for biomarkers ^e
Cycle 2 Day 1(± 3 days)	Predose ^d	GDC-9545 PK (plasma)
Surgery ^f	NA	Fresh post-treatment tumor tissue samples for biomarkers ^g
		Plasma for biomarkers ^f
End of study visit	28 days after the final dose of study treatment	GDC-9545 PK (plasma)
		Plasma for biomarkers

FFPE = formalin-fixed, paraffin-embedded; NA = not applicable; OCT = optimal cutting temperature; PK = pharmacokinetic; WGS = whole genome sequencing.

- ^a See Section 4.5.10 for details on tumor tissue sample requirements.
- ^b Optional pretreatment tumor biopsy for patients who have provided written informed consent, have an accepted archival tumor tissue sample, and if collection of tumor biopsy sample is deemed clinically feasible. One freshly frozen OCT core-needle biopsy is requested.
- ^c Not applicable for a site that has not been granted approval for WGS.
- ^d Same day as treatment administration (within 2 hours before dosing).
- ^e During treatment, fresh tumor biopsy sample and plasma for biomarkers should be collected after the last dose of treatment during the window-of-opportunity phase of the study. Tumor biopsy collection must occur prior to entry into the neoadjuvant phase of the study and any palbociclib administration. See Section 4.5.10 for details on tumor tissue sample requirements.
- ^f Refer to [Appendix 1](#).
- ^g Fresh post-treatment tumor (FFPE and non-FFPE) tissue surgical and plasma samples should be obtained within a maximum of 14 days after the last cycle in the neoadjuvant treatment phase and ideally should occur as soon as possible after the last dose of study treatment. Post-treatment plasma sample for biomarkers should be collected prior to surgery. See Section 4.5.10 for details on tumor tissue sample requirements; see Section 4.5.16 for details on an optional tumor biopsy collected at end of treatment.

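### Appendix 1 footnote c puts control-arm anastrozole on Days 1–21 of each neoadjuvant cycle; the synopsis, Section 4.3.2.1 and the Appendix 1 table row put it on Days 1–28

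*Combined protocol and SAP*

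**What the plan says.** Four places state the days on which anastrozole is given in the neoadjuvant phase.

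- **Synopsis (Test Product) and Section 4.3.2.1**, in identical words: "GDC-9545 30 mg PO QD or anastrozole 1 mg PO QD will be administered on Days 1–28 of each 28-day cycle". Palbociclib is on Days 1–21.
- **Appendix 1, drug row of the table**: "GDC-9545 or anastrozole (QD Days 1–28 of each cycle". Palbociclib has its own row, on Days 1–21.
- **Appendix 1, footnote c**, attached to the heading of the neoadjuvant column: "anastrozole 1 mg PO QD (Days 1–21/cycle) plus palbociclib 125 mg PO QD (Days 1–21/cycle) for four cycles". The first half of the same sentence keeps the experimental drug on the full cycle: "Patients will receive GDC-9545 30 mg PO QD (Days 1–28/cycle) plus palbociclib 125 mg PO QD (Days 1–21/cycle".

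Nothing in the protocol provides for a planned break in anastrozole, and Section 5.1.4.1 allows no change to its dose. Three later rules depend on the schedule or on the date of the last dose:

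- Section 4.3.2.2: "Treatment compliance will be defined as the number of capsules or tablets taken divided by the expected number of capsules or tablets".
- Section 6.5.1: "Drug exposure will also be summarized, including duration of treatment, cumulative dose, and dose intensity".
- Section 5.3.1: "After initiation of study drug, all adverse events will be reported until 28 days after final dose of study treatment".

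**The concern.** Appendix 1 contradicts itself: its table row and its footnote give different comparator regimens. The footnote is a complete sentence of current text, so neither a broken table nor superseded wording explains it. I found no rule saying which text prevails.

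The discrepancy is one-sided. GDC-9545 is on Days 1–28 wherever its schedule is given, so a site that followed the footnote would under-dose only the control arm, ahead of objective response (secondary), Ki67, cell cycle arrest and pathological complete response at surgery (exploratory), and neoadjuvant-phase safety. Any resulting weakening of control-arm efficacy would favour GDC-9545.

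A reader might not notice the slip. Section 4.3.2.1 refers to Appendix 1 for in-clinic administration. Section 3.1, to which Section 4.3.2 points for the regimens, gives no anastrozole days. Sections 3.1 and 4.5.7 also place the final ultrasound after Day 21 of Cycle 4, linking it to the final combination dose, which could make a Day 21 stop look deliberate.

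**Working it through.** The plan has no figure of its own to reproduce here. The check compares the texts and then counts planned doses.

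**Inputs.** Four 28-day neoadjuvant cycles and a 14-day window phase (Section 3.1); anastrozole on 21 days per cycle (footnote c) or 28 (synopsis, Section 4.3.2.1, table row); about 215 patients randomized 1:1 at about 90 sites (Section 3.1).

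**Planned anastrozole doses per patient**

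| | Footnote c | Other three places | Shortfall |
|---|---|---|---|
| Neoadjuvant phase | 4 × 21 = 84 | 4 × 28 = 112 | 28 doses; 1 − 84/112 = 25% |
| With window phase | 14 + 84 = 98 | 14 + 112 = 126 | 28 doses; 1 − 98/126 = 22.2% |

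**Compliance (Section 4.3.2.2), if dosing and denominator come from different texts**

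- Dosed by the footnote, 28-day denominator: 84/112 = 75%.
- Dosed on 28 days, footnote denominator: 112/84 = 133%.

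**Last dose and adverse event window**, counted from Cycle 0 Day 1 with no delays

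- Footnote: last dose on day 14 + 84 + 21 = 119; window closes on day 119 + 28 = 147.
- Days 1–28: last dose on day 14 + 112 = 126; window closes on day 126 + 28 = 154.
- The window, and the end of study visit tied to the last dose, would come 7 days earlier.

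**Time off endocrine therapy at surgery.** Sections 3.1 and 4.5.11 allow surgery up to 14 days after the final cycle. Counted from Cycle 4 Day 28, the longest gap is 14 days on the full schedule and 7 + 14 = 21 days on the footnote schedule. Footnote d counts from the final treatment instead, which would cap the gap at 14 days on either schedule.

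**Trial level.** The documents do not say how many sites would follow the footnote. Assume control patients are spread evenly: (215/2)/90 = 1.19 per site. The mean control-arm shortfall in neoadjuvant dosing days is then:

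- 1 site: 25% × 1/90 = 0.28%
- 10 sites: 25% × 10/90 = 2.8%
- all 90 sites: 25%

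These figures bound the arithmetic; they do not forecast what sites will do.

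**What is not affected.** Appendix 2, footnote e, requires of the Week 2 sample: "Tumor biopsy collection must occur prior to entry into the neoadjuvant phase of the study and any palbociclib administration". The primary endpoint and Week 2 cell cycle arrest are therefore fixed before the discrepancy can act. The sample size rests on the primary endpoint alone.

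**The case against.** The best reply is that the intended regimen is plain. Three statements outvote one, and they include the dosing section and the table row that a site reads for administration. That row groups anastrozole with GDC-9545 and lists palbociclib separately. Footnote c itself goes on to describe 28-day cycles. Section 4.3.2 sends sites to Section 3.1, Figures 1 and 2 and the pharmacy manual for regimens and administration, not to a footnote; Figure 2 and the manual were not available for checking and may well be right. On this view every consequence is conditional on a site following the footnote against the main text, the site counts are arbitrary, and the 133% figure needs a denominator that Section 4.3.2.2 does not imply. The shift in the adverse event window merely follows from each patient's actual last dose. A patient dosed on Days 1–21 would also have followed approved protocol wording, so how to classify the case is debatable.

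Much of this stands. Intent is clear, most sites would probably dose correctly, and nothing shows that any site did otherwise. The window shift is a knock-on effect and not a separate defect. But none of it makes the footnote right. It is a literal comparator dosing statement in the schedule of activities, and that the reader can infer the intent is no reason to leave it in place.

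**Conclusion.** The concern holds. Footnote c misstates the comparator regimen and should be corrected, although it does not threaten the trial's main conclusion. For a control patient who follows it, the cost is 28 of 112 neoadjuvant doses (25%), in four 7-day gaps that the experimental arm does not have. Across the control arm, the mean shortfall lies anywhere from near zero to 25%, depending on site behaviour that the documents do not reveal. They also give no figure for the effect of a 7-day anastrozole gap on tumour size or Ki67, so no bias in objective response is claimed. The day counts assume four full cycles without delay.

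**What to change.** 1. In Appendix 1 footnote c, change the anastrozole days from 1–21 to 1–28.
2. Send sites a short clarification, and check that Figure 2 and the pharmacy manual agree.
3. State that expected tablets (Section 4.3.2.2) and dose intensity (Section 6.5.1) are derived from the Days 1–28 schedule.
4. Identify any control patient already dosed on Days 1–21 and record this as a protocol deviation, noting that the protocol's own wording was the source. How to grade it under Section 9.2 is the sponsor's decision.

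The cost is one changed number and a site notice. The sample size, primary endpoint and primary test stay as they are.
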